4.4 Subject enrollment and randomization

Each subject enrollment must be approved by the study sponsor or designee before randomization can take place (see separate study manual). Key eligibility criteria must be made available.

Randomization is recognized as an appropriate means to minimize bias in subject selection for efficacy assessment in clinical trials with 2 (or more) treatment arms. The randomization schedule will be prepared using a blocked randomization scheme. A unique subject number will be assigned at the time of randomization that will be used to identify the subject throughout the clinical study and must be used on all study documentation related to that subject.

To minimize potential imbalances between groups in subject characteristics that may influence the study results randomization will be stratified by $\beta 2$ microglobulin levels ($< vs \geq 3$ mg/L), prior lines of anti-MM treatment (3 vs >3) and subjects' age ($\leq vs >75$ years).

4.5 Blinding

As this is an open-label study, there is no blinding for treatment assignment, but any review of the collective data will be performed in a blinded manner.

4.6 Treatment

See chapter 6.

4.7 Long-Term Follow Up

After completion of the PFS phase of the study, subjects will be followed for survival status by telephone contact or other method every 2 months for 2 years from disease progression. Long-term follow-up will continue until the subject has withdrawn consent for further participation, is lost to follow-up, has died, or the Sponsor makes a decision to close the study. For any subject who is lost to follow-up,

the study site will attempt to ascertain survival information via public database search. Informed consent to obtain these data will be obtained from subjects at the time of enrollment.

4.8 Premature Termination of the Trial

If the sponsor, the Lead Principal Investigators, or the Data Monitoring Committee discovers conditions arising during the trial, which indicate that the clinical investigation should be halted, the trial can be terminated after appropriate consultation the aforementioned parts. The Regulatory Authorities and Independent Ethics Committees/Institutional Review Board will be notified in writing. The reason will be stated.

Conditions that may warrant termination of the trial include, but are not limited to the following:

- The discovery of an unexpected and significant or unacceptable risk to the patients enrolled in the trial
- The discovery of lack of efficacy
- Failure of the investigators to enter patients at an acceptable rate in the trial as a whole
- A decision on the part of the Sponsor to suspend or discontinue development of the drug.

5. SUBJECT SELECTION AND WITHDRAWAL

5.1 Number of subjects and study sites.

Approximately 250 subjects will be enrolled (125 in each arm), in 20 different sites in North America and Europe.

5.2 Inclusion criteria

- Age \geq 18 years when signing the informed consent form (ICF).
- The subject must understand and voluntarily sign the ICF prior to any study related activities.
- Must be able to adhere to the study visit schedule and other protocol requirements
- Subjects must have documented and measurable Symptomatic multiple myeloma.
- Subjects must have had at least 2 prior regimens of anti-MM therapy, including lenalidomide and bortezomib.
- Subjects must have documented relapsed disease during or after their last treatment. Subjects refractory to the most recent line of therapy are also eligible. Relapse is defined as progression of disease after an initial response to previous treatment, more than six months after cessation of treatment. Refractory is defined as resistance to treatment due to lack of response or progression of disease during treatment or within six months after cessation of treatment.
- Platelet count \geq $50 \times 10^9/L$.
- Hemoglobin \geq 8 g/dL (80 g/L) within 21 days prior to randomization (subjects may be receiving red blood cell transfusions in accordance

with institutional guidelines).

- Absolute neutrophil count $\geq 1.0 \times 10^9/L$ within 21 days prior to randomization.
- Life expectancy > 3 months.
- Eastern Cooperative Oncology Group (ECOG) performance status: 0-2.
- Females of childbearing potential must agree to ongoing pregnancy testing and to practice contraception.
- Male subjects must agree to practice contraception.
- All subjects must agree not to share medication.

5.3 Exclusion criteria

- Subjects with severe renal impairment (Creatinine Clearance <30 ml/min).
- Subjects with prior history of malignancies.
- Prior pomalidomide treatment.
- Use of other investigational anti-MM agents 21 days prior to randomization.
- Any condition that would place the subject at unacceptable risk if participated in the study.
- Pregnant or breastfeeding females.
- Discontinuation of previous lenalidomide or dexamethasone treatment due to intolerance.
- Chemotherapy or investigational agent within 3 weeks prior to randomization or antibody therapy within 3 weeks prior to randomization.
- Pregnant or lactating females.
- Acute active infection requiring treatment (systemic antibiotics, antivirals, or antifungals) within 14 days prior to randomization.
- Known human immunodeficiency virus infection.
- Active hepatitis B or C infection.
- Ongoing graft-vs-host disease.
- Any other clinically significant medical disease or condition that, in the Investigator's opinion, may interfere with protocol adherence or a subject's ability to give informed consent.

Eligibility criteria for this study have been carefully considered to ensure the safety of the study subjects and to ensure that the results of the study can be used. It is imperative that subjects fully meet all eligibility criteria.

5.4 Subject withdrawal (from medicine and/or trial)

A patient should be withdrawn from treatment with investigational drug if at any time:

- It is the wish of the patient (or their legally acceptable representative) for any reason.
- The investigator judges it necessary due to medical reasons.
- Patient becomes pregnant.
- Patient experience a Critical Adverse Event.

A patient should be withdrawn from the study at any time if:

- It is the wish of the patient (or their legally acceptable representative) for any reason.

- The investigator judges it necessary due to medical reasons.
- In case of disease progression.
- The patient receives prohibited therapy or procedures during the study.

6. TREATMENTS

6.1 Treatment Characterization

Investigational Product

An investigational product, also known as investigational medicinal product in some regions, is defined as follows: A pharmaceutical form of an active substance or placebo being tested or used as a reference in a clinical study, including products already with a marketing authorization but used or assembled (formulated or packaged) in a way different from the authorized form, or used for an unauthorized indication, or when used to gain further information about the authorized form. The investigational product should be stored in a secure area according to local regulations. It is the responsibility of the investigator to ensure that investigational product is only dispensed to study subjects. The investigational product must be dispensed only from official study sites by authorized personnel according to local regulations.

In this protocol, investigational product is pomalidomide.

Non-investigational Product

Other medications used in the study as support or escape medication for preventative, diagnostic, or therapeutic reasons, as components of the standard of care for a given diagnosis, are considered non-investigational products.

In this protocol, the non-investigational product is dexamethasone.

6.2 Treatment description

Pomalidomide is a potent immunomodulatory drug in the same class as thalidomide and lenalidomide. It has proven antimyelomatic properties in RRMM patients either as monotherapy or in combination with Low-dose dexamethasone (33) regardless of prior lenalidomide and bortezomib treatment (relapsed and refractory) (34).

Pomalidomide will be supplied by the Sponsor as 1, 2, 3, 4, mg capsules for oral administration. It will be packaged in bottles containing 21-day supply (1 cycle) and should be stored as labeled, accessible exclusively to study personnel.

Dexamethasone is commercially available and for this study it will be prescribed to the subjects.

6.3 Treatment administration and Schedule

Subjects randomized to Pom/dex:

Oral pomalidomide, 4 mg/day on days 1-21 out of a 28-day cycle.

Subjects should take their dose as close to every 24h as possible. If the dose is delayed more than 6 hours, it should be skipped and considered missed.

PO or IV Low-Dose Dexamethasone, 40 mg/day (20 mg for >75 years) PO or IV on days 1, 8, 15, 22 out of a 28-day cycle.

Subjects randomized to DEX:

PO or IV High-Dose Dexamethasone, 40 mg on days: 1-4, 9-12, 17-20 out of a 28-day cycle.

6.4 Treatment overdose, dose delay and interruption/discontinuation

Overdose, as defined in this protocol, refers to pomalidomide dosing only.

It is defined as any amount over the specified dose or anything more frequently than the required schedule of frequency.

6.5 Dose Delay, Interruption, or Discontinuation

If the dose of one drug in the regimen (ie, pomalidomide or dexamethasone) is delayed, interrupted, or discontinued, the treatment with the other drugs may continue as scheduled.

Subjects experiencing a 28 day delay in all study drugs (pomalidomide and low-dose dexamethasone) due to an adverse event(s) related to study treatment must be discontinued from study drug. Subjects experiencing delays unrelated to study therapy, for example due to radiation therapy may delay study treatment up to 42 days. Delays greater than 28 days must be discussed with the medical monitor.

Patients are considered still on study therapy even if they continue solely on pomalidomide.

6.6 Dose modifications

Dosing interruption and titration is permitted during the study, Subjects will be evaluated for AEs at each visit. The severity of AEs will be measured. Thus, the dose can be modified if a subject experiences a dose-limiting toxicity (DLT).

Pomalidomide dosing can be reduced to 1 mg starting from 4 mg, in 1 mg increments.

If an AE is resolved in 28 days, then pomalidomide can be re-initiated at full dose. If not, then the dose should be decreased by one increment.

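### Section 6.6 ties the restart of pomalidomide to an undefined full dose, so a subject already reduced for toxicity may, though need not, go back to 4 mg after a further toxicity

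*Protocol*

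**What the plan says.** Protocol Section 6.3 assigns the dose: "Oral pomalidomide, 4 mg/day on days 1-21 out of a 28-day cycle". Sections 1.4 and 4.1 give the same 4 mg, and no other pomalidomide dose is assigned anywhere.

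Section 6.6 allows the dose to be modified for a dose-limiting toxicity and sets the ladder: "Pomalidomide dosing can be reduced to 1 mg starting from 4 mg, in 1 mg increments". A two-part rule follows. The first part covers recovery: "If an AE is resolved in 28 days, then pomalidomide can be re-initiated at full dose". The second covers non-recovery: "If not, then the dose should be decreased by one increment".

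The term full dose appears only in this rule and is not defined.

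Three other places bear on the point:

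- Section 6.5 brings in the medical monitor for long holds: "Delays greater than 28 days must be discussed with the medical monitor". It also requires discontinuation when all study drugs are delayed 28 days for a treatment-related AE, and it allows one drug to be held or stopped while the other continues.
- Section 5.4 has the drug withdrawn when "The investigator judges it necessary due to medical reasons".
- Section 6.2 lists the strengths: "Pomalidomide will be supplied by the Sponsor as 1, 2, 3, 4, mg capsules for oral administration".

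**The concern.** A dose-reduction ladder protects a subject only if a reduction made for toxicity stays in force. Section 6.6 does not say that it does. The restart level is a term that most naturally points to the assigned 4 mg, because that is the only dose the protocol gives. On that reading, a second toxicity that clears within 28 days opens the way to a higher dose than the one at which it arose.

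At stake are subject safety in the Pom/dex arm and consistent dosing: two sites could handle the same case differently and both comply. Sample size, power, alpha and the planned analyses are not involved.

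**Working it through.** There is no plan figure to reproduce. The check traces the rule and adds simple dose arithmetic.

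**Inputs**

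- Assigned dose 4 mg/day on 21 days of each cycle (Section 6.3).
- Ladder 4, 3, 2, 1 mg (Section 6.6).
- AE resolved within 28 days: restart at full dose allowed. AE not resolved: one step down (Section 6.6).
- Medical monitor consulted only for delays over 28 days (Section 6.5).
- Planned median PFS of 3 months in the Pom/dex arm (Section 9.4).

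**Step 1: trace the rule.** A subject on 4 mg has an AE that is not resolved at 28 days and steps down to 3 mg. A later toxicity on 3 mg resolves within 28 days. The restart sentence now applies. Read as 4 mg, it permits a return to the level already lowered for toxicity. The same path is open from 2 mg and from 1 mg. A hold of up to 28 days does not reach the Section 6.5 requirement to consult the medical monitor.

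**Step 2: size of the dose rise.** Dose per cycle = 21 days × level, so 4 mg gives 21 × 4 = 84 mg.

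| Level at AE onset | Dose per cycle | Restart at 4 mg | Restart at pre-hold level |
|---|---|---|---|
| 3 mg | 21 × 3 = 63 mg | 84 − 63 = +21 mg; 84/63 = 1.33 (+33%) | 0% |
| 2 mg | 21 × 2 = 42 mg | 84 − 42 = +42 mg; 84/42 = 2.00 (+100%) | 0% |
| 1 mg | 21 × 1 = 21 mg | 84 − 21 = +63 mg; 84/21 = 4.00 (+300%) | 0% |

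The dose never exceeds the assigned 4 mg.

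**Step 3: how easily each row is reached.** By the step-down sentence alone, each decrement needs an AE unresolved at 28 days:

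- 3 mg: 1 × 28 = 28 days at least.
- 2 mg: 2 × 28 = 56 days at least.
- 1 mg: 3 × 28 = 84 days at least, about 2.8 months, before any time on drug is counted.

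Set against a planned 3-month median PFS, the 1 mg row would be uncommon by this route. The 3 mg row needs only one earlier reduction. Section 6.6 also lets the dose be modified for a dose-limiting toxicity without stating a 28-day wait, so a reduction can come sooner.

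**Step 4: the floor.** At 1 mg, one step down gives 1 − 1 = 0 mg. That is below the stated range and below the smallest capsule, and Section 6.6 names no action for it.

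**The case against.** The best defence reads the two parts of the rule as a pair. The second part works from the subject's current dose, so the first may simply mean a restart without a decrement. The 4 mg reading also gives an odd result: at 2 mg, a resolved AE leads to 4 mg and an unresolved one to 1 mg. This makes the pre-hold reading plausible, and under it nothing goes wrong. It does not make that reading the stated one: full dose is an unusual term for a reduced dose, and no sentence says that reductions persist.

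The wording is also permissive. A reader might infer that the protocol sends reduced subjects back to 4 mg; it does not. The restart is something that can be done, AEs are reviewed at each visit, and Section 5.4 has the drug withdrawn on the investigator's medical judgement. This limits the harm, but Section 5.4 sets no restart level.

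A reader might also infer that a subject who cannot tolerate 1 mg is left without protection. That is too strong. A pomalidomide hold that runs past 28 days must go to the medical monitor under Section 6.5. That section contemplates stopping one drug alone, and it requires discontinuation when all study drugs are delayed 28 days for a related AE. Stopping is the evident step at a 1 mg floor, so only an explicit sentence is missing.

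Finally, whether re-escalation after recovery should ever be allowed is a clinical choice. That is true, but it should then be written as a deliberate rule rather than left to an undefined term.

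**Conclusion.** The point stands as a minor-to-moderate safety wording correction. Section 6.6 permits, without requiring, a restart at 4 mg in a subject already reduced for toxicity, with no medical-monitor contact when the hold is 28 days or less, and it leaves room for sites to differ.

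The rises of 33%, 100% and 300% rest on reading full dose as 4 mg; on the pre-hold reading the rise is 0%. They are ratios of dose levels, not expected effects. The protocol gives no rate of dose reductions, so the number of subjects affected cannot be estimated.

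Two stronger inferences are not supported. The restart sentence is not shown to contradict Section 6.5: the defect is an undefined restart level, which Section 6.5 does not address. Nor do the documents show any effect on the PFS or OS comparison, power or alpha.

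**What to change.** In the last paragraph of Section 6.6, replace the words *at full dose* with: *at no more than the dose level in use at AE onset; earlier reductions for toxicity persist*.

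Add for clarity: *if a further decrement is due at 1 mg, discontinue pomalidomide*.

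The cost is a short protocol amendment with site retraining. No extra subjects or data are needed, and no new supply, since Section 6.2 already provides every capsule strength on the ladder. The downside is slightly lower dose intensity in subjects who would otherwise be re-escalated. If the sponsor does want re-escalation in some cases, Section 6.6 should state when it is allowed and who must agree.

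### After a 28-day hold of both Pom/dex drugs for an unresolved related AE, Section 6.5 stops study drug while Section 6.6 lowers pomalidomide one step, and neither takes precedence

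*Protocol*

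**What the plan says.** Section 6.5 of the protocol (dose delay, interruption or discontinuation) deals separately with a hold of one drug and a hold of the whole regimen.

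- **One drug held.** If either drug "is delayed, interrupted, or discontinued, the treatment with the other drugs may continue as scheduled".
- **Both drugs held, related AE.** The group is defined as "Subjects experiencing a 28 day delay in all study drugs (pomalidomide and low-dose dexamethasone", and those whose delay is "due to an adverse event(s) related to study treatment must be discontinued from study drug".
- **Both drugs held, cause unrelated to study therapy.** Treatment may be delayed for up to 42 days.
- **Medical monitor.** "Delays greater than 28 days must be discussed with the medical monitor".

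Section 6.6 (dose modifications) sets the pomalidomide steps: "Pomalidomide dosing can be reduced to 1 mg starting from 4 mg, in 1 mg increments". It then gives a rule for day 28. "If an AE is resolved in 28 days, then pomalidomide can be re-initiated at full dose". The next sentence covers every other outcome: "If not, then the dose should be decreased by one increment".

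**The concern.** Both sections act at 28 days, and their scopes overlap. Section 6.5 depends on which drugs were held and why. Section 6.6 depends only on whether the AE has resolved. A subject can therefore meet both conditions at once and receive two instructions that cannot both be carried out: stop study drug, or carry on with pomalidomide at a lower dose.

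The stake is patient safety and uniform conduct. Such a subject has had the whole regimen withheld for four weeks because of drug-related toxicity that is still present. A site working from Section 6.6 could expose that subject to pomalidomide again when Section 6.5 forbids it. Section 5.1 plans 20 sites in North America and Europe, so a mandatory stop should not depend on each site drawing the same inference.

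**Working it through.** No sample-size, power or alpha figure bears on this point, so the check compares the two rules case by case.

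**Inputs**

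- Section 6.5 stop rule: all study drugs delayed, 28 days, AE related to treatment. The action is mandatory discontinuation.
- Section 6.6 reduction rule: AE not resolved at 28 days. The action is one increment down. It has no condition on which drugs were held or on relatedness.
- Section 6.6 dose levels: 4, 3, 2 and 1 mg.
- Section 5.1: 125 subjects per arm.

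**Step 1: the four cases for an AE unresolved at day 28**

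| Drugs held | AE related? | Section 6.5 | Section 6.6 | Conflict? |
|---|---|---|---|---|
| Pomalidomide only | Yes | Stop rule not triggered; dexamethasone may continue | Reduce one step | No |
| Pomalidomide only | No | Stop rule not triggered; dexamethasone may continue | Reduce one step | No |
| Both | No | Delay allowed up to 42 days; no stop at day 28 | Reduce one step | No stop-versus-reduce conflict |
| Both | Yes | Must stop study drug | Reduce one step | **Yes** |

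**Step 2: the dose at issue in the conflicting case**

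| Dose before the hold | Under Section 6.5 | Under Section 6.6 |
|---|---|---|
| 4 mg | 0 mg | 4 − 1 = 3 mg |
| 3 mg | 0 mg | 3 − 1 = 2 mg |
| 2 mg | 0 mg | 2 − 1 = 1 mg |
| 1 mg | 0 mg | no lower level defined |

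**Step 3: does other text settle the order?**

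- Neither section refers to the other.
- The medical monitor sentence covers delays longer than 28 days. It says whom to consult but not what to decide, and it does not reach a restart at day 28 itself.
- Section 5.4 lists grounds for withdrawal, including the investigator's medical judgement and a critical AE, but does not rank the two rules.
- Section 6.5 ends by counting a patient who takes pomalidomide alone as still on therapy. That makes a reduced-dose restart of pomalidomide look acceptable.

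**Step 4: who is exposed, and what reaches the analysis**

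Section 6.5 names the two drugs of the Pom/dex regimen, so only that arm (125 planned) can be affected. The primary analysis includes all randomized subjects (Section 9.2). Stopping drug is neither a PFS event nor a censoring point in Section 3.3. Section 4.1 keeps subjects who stop for toxicity under assessment until progression.

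One secondary link exists. Section 4.1 assesses those subjects twice monthly, while Sections 4.3 and 7.2 assess on Day 1 of each 28-day cycle. The rule a site chooses can therefore change how often progression is looked for in that subject. With no rate of such holds in the protocol, this effect cannot be sized.

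**The case against.** The best reply is that ordinary reading already settles the order. Section 6.5 is narrow and mandatory; Section 6.6 is a general titration rule in weaker terms. A subject who has to stop has no dose left to adjust.

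A second reply is that the last sentence of Section 6.6 gives no restart day and does not expressly order dosing while the AE continues. It may only fix the dose level for a later restart, leaving Section 6.5 to decide whether a restart is allowed. A third is that a hold running past day 28 must go to the medical monitor, and the investigator can always withdraw a subject on medical grounds.

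These points lower the likelihood of harm, and most sites would probably follow Section 6.5. They do not remove the fault. Neither reconciliation is written down. Confining Section 6.6 to unrelated AEs is also strained, because that section introduces dose changes for dose-limiting toxicity, which naturally means drug toxicity. The safeguards rely on consultation and judgement, whereas Section 6.5 sets a fixed stop. It is fair to add that no trial-level effect on the results has been shown.

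**Conclusion.** The concern holds. In one of the four cases at day 28, namely both drugs held for a related AE that is still present, the protocol gives two incompatible instructions and no precedence. For a subject held from 4 mg/day the difference is 0 versus 3 mg/day; from 3 mg it is 0 versus 2 mg, and from 2 mg it is 0 versus 1 mg.

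The conclusion rests on reading Section 6.6 as written, without an unstated limit to pomalidomide-only holds or to unrelated AEs. No count of affected subjects is claimed. The planned PFS test, its power and its alpha are untouched. The text should be corrected because the error, where it occurs, runs toward renewed exposure during unresolved drug toxicity.

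**What to change.** Replace the last sentence of Section 6.6 with wording such as:

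> If not, lower pomalidomide by one increment, unless Section 6.5 requires discontinuation (all study drugs delayed 28 days for a related AE).

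This keeps the mandatory stop in Section 6.5 and leaves Section 6.6 to govern when only pomalidomide is held. The cost is one sentence, made through the amendment route in Section 11.2. It has no statistical cost.
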